### 7.4 Exclusion Criteria

A patient who meets any of the following criteria is not eligible to participate in the study:

1. Prior surgical treatment of the nasal valve
2. Rhinoplasty, septoplasty, inferior turbinate reduction or other surgical nasal procedures within the past twelve (12) months
3. Severe and/or chronic sinusitis, recurrent sinusitis, or allergies leading to nasal obstruction and currently requiring oral corticosteroid therapy
4. Severe case of any of the following; septal deviation, turbinate hypertrophy, polyps, or ptotic nose tip believed to be the primary contributor to the subject's nasal obstruction symptoms and warranting surgical intervention
5. Known or suspected allergies or contraindications to the anesthetic agents and/or antibiotic medications to be used during the study procedure session
6. Known or suspected to be pregnant, or is lactating
7. Other medical conditions which in the opinion of the investigator would predispose the subject to poor wound healing or increased surgical risk.

## 8.0 STUDY PHASES

[figure not shown]
The study will be conducted in four phases as subjects are consented, evaluated for eligibility, treated and followed until study exit:

Phase 1 - Pre-Screen / Informed Consent Process

Phase 2 - Screening / Baseline Evaluation

Phase 3 - Enrollment / Study Procedure

Phase 4 - Follow-up / Study Exit

The different study phases are described in Sections 8.1 through 8.4. Section 8.5 provides a table of required study visits, the visit windows, and the assessments to be done at each visit, as well as a description of each assessment type.

### 8.1 Phase 1: Pre-Screen and Informed Consent Process

Patients presenting with symptoms associated with nasal airway obstruction will be approached with the study and asked if they are willing to volunteer participation. Patients will initially be asked about duration of symptoms and conservative measures used for their condition. Any known concomitant nasal conditions and past nasal surgeries will be discussed to understand if they are potential candidates for the study.

#### Informed Consent

Informed consent will be obtained as outlined in 21 CFR Part 50 and the Good Clinical Practice: Consolidated Guidance (ICH, April 1996).

A research study member at the approved study site will speak with the study candidate about the purpose of the study and investigational research. Explanation of the study background, study procedure, follow up visit schedule, study procedure risks and benefits will be reviewed in detail with the patient. Patients will be given the time they need to read through the study information and informed consent document and ask as many questions as necessary to make them comfortable with the study and the requirements. For those potential candidates who agree to participate in the study by signing the IRB approved Informed Consent Form (ICF), a baseline evaluation will be conducted.

### 8.2 Phase 2: Screening and Baseline Evaluation

During the screening/baseline visit in the study clinic, the Investigator or designated research staff will perform a formal evaluation of the study candidate for study eligibility, which will include a history and physical examination of the nasal area, review of overall medical history, understanding of general health and discussion of any conservative measures used for nasal airway obstruction.

The following data will be collected:

- Patient demographics
- Medical history including prior tests and treatments for nasal airway obstruction
- Physical exam and vital signs
- NOSE questionnaire (completed by the subject)
- Investigator visual assessment (using an endoscope) of nasal valve area to be treated

Subjects who agree to participate and meet the enrollment criteria must be scheduled to undergo the study procedure **within 30 days** of the baseline visit.

### **8.3 Phase 3: Enrollment and Study Procedure**

Study subjects will be considered enrolled once they arrive at the study clinic to undergo the investigational procedure. At this time a study subject identification number will assigned along with the study subject binder. The investigational procedure will be performed in the study clinic. Subjects will have both nasal valves treated in a single study procedure session. Each nostril will be treated at up to 3 non-overlapping positions along the upper lateral nasal valve region.

Treatment settings to be used are:

Temperature ..... 60°C

Power ..... 4 Watts

Treatment Time ..... 18 secs

Cooling Time ..... 12 secs

No repeat ("touch-up") procedures will be permitted during the 26-week follow-up period. Follow-up visit dates will be calculated from the study procedure date. Follow-up visits should be scheduled within the specified visit windows described in Table 1.

#### Immediate Post-Procedure Care (prior to leaving the clinic)

Subjects will be asked to mark a vertical line on a 10 cm VAS scale to represent the pain level experienced on the Left Side and a separate VAS for pain experienced on the Right Side during the study procedure session. The score will include the overall pain experience from anesthesia delivery to procedure completion.

At the discretion of the physician, the following care may be provided:

- Apply compression to the treatment area with or without topical anesthetic, internally for 5 minutes.
- Apply petroleum jelly to the treatment area as needed.
- The patient should be instructed not to manipulate the treatment site for 24 hours with the exception of any necessary hemostasis.

Study subjects will be reminded of their next follow-up visit and will be scheduled within the study window.

**8.4 Phase 4: Follow-Up and Study Exit**

The follow-up period will begin after the study procedure session. Subjects will undergo follow-up visits at **4 weeks, 12 weeks, and 26 weeks** calculated from the study procedure date. Requirements for each follow-up visit are provided in Table 1. Subjects that meet the study requirements as planned will be exited from the study at the 26-week follow up visit.

If a subject reaches the 26-week follow-up visit and is experiencing a new or ongoing adverse event, the study sponsor should be contacted to discuss the need and/or methods for continued surveillance of the event.

**8.5 Types of Assessments**

Table 1 outlines the assessments to be performed at each required visit, and specifies the required visit windows.

The following assessments will be obtained from the study subjects at the specified study follow-up visits:

Visual Assessment of Treatment Area – The target nasal valve area within each nostril will be visually assessed at baseline and following the treatment procedure at the time points described in Table 1. The use of an endoscope for visual assessment is required. For consistency in reporting across sites, a study CRF will outline specific observations to be assessed. In addition, representative still photographs of each nostril will be captured at each visit.

Nasal Obstruction Severity Evaluation (NOSE) Scale – The NOSE Scale is a validated disease-specific health status instrument to measure the outcome of subjects treated for nasal obstruction. This outcome assessment has been used to measure improvements in QOL in septoplasty, functional septorhinoplasty and nasal valve surgery (Rhee, Weaver et al. 2010). The NOSE Scale will be utilized to evaluate the severity of the subject's nasal obstruction at baseline and follow-up time points.

Visual Analog Scale (VAS) for Pain Intensity – The Pain VAS will be used to rate pain associated with the treatment (Hawker, Mian et al. 2011). Subjects will be asked to mark their pain level on a 10 cm line anchored by verbal descriptors: 0 = no pain and 10 = worst pain imaginable. The study staff will measure with a metric ruler from the 0, the beginning of the line, to the vertical mark made by the subject. The result, expressed in millimeters, will represent the subject's VAS Pain Score.

Adverse Event Evaluation – Subjects will be asked about possible side effects or adverse experiences related to the study procedure. All events will be documented on the proper Adverse Event Log and Adverse Event Case Report Form. Anticipated observations related to the study procedure will be tabulated, but will not be categorized as adverse events unless they require

mitigation by the treating physician or are greater in severity, duration or degree of incidence than anticipated. Refer to Table 2 for a listing of anticipated observations as well as anticipated frequency, severity and duration.

**Medications** – Updates to current medications or any new or changed medications will be requested at each follow-up visit. The medication log will be updated to reflect any changes. In addition, any medications required as a result of intervention related to the study procedure will be documented and will correlate with the Adverse Event Case Report Form.

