## 11.0 ADVERSE EVENTS

Adverse events (AEs) may occur during the treatment phase or during the follow-up phase. Adverse events occurring after the baseline assessment but before the treatment procedure will be documented in the subject's medical record but will not count as related to the investigational device or procedure.

Each adverse event will be recorded in the corresponding subject's CRF. Each adverse event will be judged by the Investigator as to its relationship and level of relatedness to the investigational device and/or investigational procedure. In addition, the Investigator will identify the date of onset, severity and duration of the AE. All adverse events will be monitored until they are adequately resolved or explained. If a subject reaches the 26-week follow-up visit and is experiencing a new or ongoing adverse event, the study sponsor should be contacted to discuss the need and/or methods for continued surveillance of the event.

The Investigator must submit to the Sponsor a report of any Serious Adverse Event (SAE), Serious Adverse Device Effect (SADE) or Unanticipated Adverse Device Effect (UADE) within 24 hours of knowledge of the event.

Sponsor Contact: [name]  
[contact]  
[contact]  
Email: [contact]

In addition, the Investigator will report adverse events to the reviewing IRB / EC (*as applicable*) according to the local reporting requirements.

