### 13.7 Adverse Events

All adverse events for subjects in the safety population will be reported.

- Serious Adverse Events
- Non-serious Adverse Events
- Device Related Adverse Event
- Device Related Serious Adverse Events

The following time intervals, based on the date of the procedure, will be considered:

- 0 days to 4 weeks
- 4 weeks to 12 weeks

- 12 weeks to 26 weeks

Results will include the number of subjects experiencing each type of event as well as the number of events.

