## 31.0 DEFINITIONS AND ACRONYMS

### Adverse Events

Adverse Event (AE) – any untoward medical occurrence in a subject (ISO 14155).

*NOTE: This definition does not imply that there is a relationship between the adverse event and the device under investigation.*

Serious Adverse Event (SAE) – an adverse event that (ISO 14155):

- led to a death,
- led to a serious deterioration in the health of the subject,
- resulted in a life-threatening illness or injury,
- resulted in a permanent impairment of a body structure or a body function,
- required hospitalization or prolongation of existing hospitalization,
- resulted in medical or surgical intervention to prevent permanent impairment to body structure or function,
- led to fetal distress, fetal death, a congenital abnormality, or birth defect.

Adverse Device Effect (ADE) – any untoward and unintended response to a medical device (ISO 14155)

*NOTE: This includes any event resulting from insufficiencies or inadequacies in the instructions for use or the deployment of the device. This definition also includes any event that is a result of user error.*

Serious Adverse Device Effect (SADE) – an adverse device effect that has resulted in any of the consequences characteristic of a serious adverse event or that might have led to any of these consequences if suitable action had not been taken or intervention had not been made or if circumstances had been less opportune (ISO 14155).

Anticipated Adverse Device Effect (AADE) – an adverse device effect which by its nature, incidence, severity or outcome has been previously identified in the previously identified in nature, severity, or degree of incidence in the investigational plan or application

Unanticipated Adverse Device Effect (UADE) – any serious adverse effect on health or safety or any life-threatening problem or death caused by, or associated with, a device, if that effect, problem, or death was

not previously identified in nature, severity, or degree of incidence in the investigational plan or application (including a supplementary plan or application), or any other unanticipated serious problem associated with a device that relates to the rights, safety, or welfare of subjects (21CFR812.3.s and ISO 14155).

*NOTE: The occurrence of a diagnostic or elective surgical procedure for a pre-existing condition, unless the condition becomes more severe or increases in frequency, would not be considered procedure or device-related.*

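### The adverse event question in Section 8.5 is tied to the study procedure, narrower than the all-cause events the protocol defines and reports, so some events may be under-elicited

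*Combined protocol and SAP*

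**What the plan says.** Section 8.5, under Adverse Event Evaluation, sets out what is put to subjects: "Subjects will be asked about possible side effects or adverse experiences related to the study procedure". The next sentence carries no such limit: "All events will be documented on the proper Adverse Event Log and Adverse Event Case Report Form".

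The other sections are not restricted by cause:

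- Section 31.0 defines an adverse event broadly and adds that "This definition does not imply that there is a relationship between the adverse event and the device under investigation".
- Section 11.0 states that "Each adverse event will be recorded in the corresponding subject's CRF", and then that "Each adverse event will be judged by the Investigator as to its relationship and level of relatedness" to the device or the procedure.
- Section 13.6 makes the kinds of adverse events, and how often they occur from the procedure onward, a secondary endpoint. It sets no condition on relatedness.
- Section 13.7 states that "All adverse events for subjects in the safety population will be reported", and lists device-related and serious device-related events as separate categories.

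Table 1 schedules an adverse event review immediately after treatment and at 4, 12 and 26 weeks, without saying how the review is conducted.

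**The concern.** A question framed around the procedure asks the subject to make a first judgement of cause, which Section 11.0 assigns to the Investigator. The Investigator can judge only events that come to light. A subject who has a headache or an infection some weeks later and sees no link to the treatment has no clear reason to mention it.

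Safety is half of the stated primary objective (Sections 1.0 and 7.1) and a named secondary endpoint. The trial has one arm of 50 subjects, so no comparison group would show that the counts were low. Early termination under Sections 14.0 and 24.0 also depends on the sponsor or investigator becoming aware of events. With up to 10 sites, some staff may follow the wording literally while others ask more openly, which would make capture uneven between sites.

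**Working it through.** The plan states no figure on this point, so the check is a comparison of the text at each step from enquiry to report.

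1. **Enquiry (Section 8.5).** Side effects, or adverse experiences linked to the procedure. Scope: procedure-linked on its natural reading.
2. **Definition (Section 31.0).** Any untoward occurrence, with no causal link implied. Scope: all causes.
3. **Recording (Sections 8.5 and 11.0).** All events go on the log and the case report form. Scope: all causes, once an event is known.
4. **Causality (Section 11.0).** Judged by the Investigator for each event. Scope: all recorded events.
5. **Analysis (Sections 13.6 and 13.7).** All events counted, with device-related events as separate categories. Scope: all causes.

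Step 1 is the narrowest, and steps 3 to 5 cannot recover an event that never surfaced.

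The next check is whether another route closes the gap.

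- **Adverse event review (Table 1).** Its title is unrestricted, but Section 8.5 is the text that says what it consists of.
- **Endoscopy.** Scheduled at every visit, with observations specified on the case report form. It covers the treated nasal valve area, so it finds local effects whatever the subject believes about cause, and nothing beyond that area.
- **Physical examination and vital signs.** Baseline only in Table 1.
- **Medication updates.** Requested at each follow-up visit, and able to expose an illness that was treated with a drug. The one stated link to the adverse event form concerns medications needed because of an intervention tied to the procedure, so the same limit recurs. An untreated complaint leaves no trace here.
- **Safety contacts under Section 10.0.** For some withdrawn or lost subjects these may be by phone or email. Without an examination, the question asked is most of the assessment.
- **Source data verification (Section 23.0).** Checks data; it is not described as a way of finding events.

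What remains exposed is the complaint that is non-local or untreated, that the subject does not link to the procedure and does not volunteer. The intervals add to this: the last two visits are 26 − 12 = 14 weeks apart.

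On direction and size: for a given event type, the expected number of subjects recorded is N × p × c. Here N is the number treated, p the true proportion with the event, and c the chance that it surfaces by any route. A procedure-linked question, taken literally, can only leave c the same as or lower than an open question would, so any bias in total counts is downward. The documents give neither p nor c. Table 2 reports treatment-area observations as percentages of treated nostrils in a feasibility study, and these are not capture rates. No numerical estimate is therefore offered.

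**The case against.** The strongest reply is that the governing rules are all-cause and a site that follows them must record any unrelated event it hears of. Section 11.0 even has events between baseline and treatment documented, although they cannot be due to the procedure. The wording in Section 8.5 is also open to a milder reading: the phrase about the procedure may qualify adverse experiences and not side effects, and asking about possible effects does not oblige the subject to establish cause. Section 8.5 summarises an assessment and may not be the script. The case report forms are not in the documents, and their prompt could be open. Endoscopy and medication updates give partial cover.

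Most of this stands, and it limits the point. A reader might infer that subjects are asked exclusively about procedure-related events and that all others are lost. The documents do not support that. Section 8.5 does not say that this is the sole question, volunteered events must be documented, and other routes catch some of the rest. The reply does not remove the mismatch, because no section supplies the all-cause question that the definition and the endpoint call for.

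**Conclusion.** The inconsistency is real and should be corrected. As worded, Section 8.5 may under-elicit events that subjects do not associate with the procedure, chiefly non-local or untreated ones, and total adverse event counts could be biased downward. This assumes that sites follow the sentence as written and that the case report form prompt does not already ask more broadly.

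For device-related counts the effect is possible but not established. Section 12.1 lists infection, sensory change and scarring that leads to obstruction among the potential effects, and a subject enrolled for nasal obstruction could put such a problem down to a cold or to the original condition. A reader might go further and infer that device-related rates are definitely understated. Endoscopy at every visit covers the treated area independently of what the subject believes, so that reading goes beyond the text.

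The size cannot be derived from the documents. The safety endpoint is descriptive, with counts and percentages and no success threshold, and the primary efficacy test on the NOSE score does not depend on it.

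**What to change.** Replace the sentence in Section 8.5 with an open, non-leading question, for example: has the subject had any new or worsened health problem since the last contact? Ask it at each visit where Table 1 schedules an adverse event review, and at each phone or email safety contact under Section 10.0. Change the case report form prompt to match if it now follows the Section 8.5 wording. Record every event reported, and leave relatedness to the Investigator as Section 11.0 already requires. Section 8.5 then agrees with Sections 11.0, 13.6, 13.7 and 31.0.

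The cost is one protocol sentence and perhaps one form prompt. Sample size, visit schedule and endpoints are unchanged. A few more unrelated events will be logged, and the total adverse event rate may look slightly less favourable.

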**Table 1. Schedule of Assessments**

Assessments	Screening / Baseline	Study Procedure (within 30 days of Baseline visit)	Immediately Post-Treatment	4-Week Follow-Up (+/- 7 days)	12-Week Follow-Up (+/- 10 days)	26 Weeks Follow-Up (+/- 14 days)
Demographics and Medical History	X					
Physical Exam and Vital Signs	X					
Medication Review	X	X		X	X	X
Study Procedure		X				
Endoscopic Assessment of treatment area (with representative still photographs)	X	X	X	X	X	X
NOSE Score	X			X	X	X
Subjective Pain VAS			X	X	X	
Subject Satisfaction Questionnaire						X
Adverse Event review			X	X	X	X
Pregnancy test (if female)		X				

## 9.0 SUBJECT REIMBURSEMENT

Subjects may be reimbursed for their time and travel and any expenses associated with each study visit, as allowed by study site policies. Subjects will not be reimbursed for those scheduled study visits that they do not attend.

## 10.0 STUDY WITHDRAWAL

Subjects may be terminated or withdrawn from the study for the following reasons:

- Voluntary withdrawal – meaning that the subject voluntarily chooses not to further participate in the study
- \*Lost to follow-up – meaning that the subject is more than one month late (beyond the late visit window) to a study visit and 3 documented attempts to contact the subject are unsuccessful. A subject who misses a study visit but attends a subsequent visit will no longer be considered lost to follow-up.
- \*In the physician's opinion, it is not in the best interest of the subject to continue study participation.
- Subject death.

*\*Where possible, subjects will be followed for safety to study completion. Safety follow-up will include a review of adverse events (AEs). A safety follow-up assessment may be performed either via a phone or email contact or a physician visit.*

Any study subject who does not attend a scheduled follow-up visit should be contacted by site personnel to determine the reason for the missed appointment(s). The reason for the missed visit should be determined and documented in the subject's study records. All subjects enrolled (including those withdrawn or lost to follow-up) shall be accounted for with appropriate documentation.

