## 13.0 STATISTICAL ANALYSIS

### 13.1 Sample Size Determination

Prior study data was used to estimate the expected mean change (28.5) and standard deviation (30.3) for the change in NOSE score from baseline to 6 months (26 weeks). N=45 subjects would provide 90% power to test the study hypothesis at the one-sided alpha level of 0.05. To allow for up to 10% attrition, a total of 50 subjects will be enrolled.

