### 13.2 Hypothesis Testing

The objective is to show that the mean improvement in NOSE score from baseline to 26 weeks exceeds 15 points. The null and alternative hypotheses are given by:

$$H_0: \mu_d \leq 15.0$$

$H_a: \mu_d > 15$ , where  $\mu_d$  represents the mean improvement in NOSE score from baseline to 26 weeks. The hypothesis is tested at the one-sided alpha 0.05 level.

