### 13.8.2 Handling Dropouts, Loss-to-Follow-up or Missing Data

All efforts will be made to collect all data points in this study. The study hypothesis will be tested using all available data for the subjects in the efficacy patient population. If the primary endpoint is not available for all such subjects, then additional analyses will be performed in order to assess the potential effect of missing data on the study conclusions. First an analysis will be performed, treating all missing data points for the primary endpoint as 0 improvement. If the study conclusion is upheld using this type of worst-case scenario, no other analyses will be performed. Otherwise, a multiple imputation approach will be used. The propensity method will be used including the baseline, 4 week and 12 week NOSE scores if they are available. Fifteen imputed datasets will be generated and the study hypothesis will be repeated on the imputed dataset to determine if the study hypothesis is upheld.

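### Section 10 plans contact with subjects who miss visits or are withdrawn but does not provide for collecting NOSE at that contact, so a reachable subject can end with no primary endpoint

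*Combined protocol and SAP*

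**What the plan says.** Section 10.0 lists four reasons for leaving the study. Two carry an asterisk, loss to follow-up and withdrawal on the physician's judgement, and for these the plan intends safety follow-up to study completion where possible. It names an adverse event review as the content and gives the mode: "A safety follow-up assessment may be performed either via a phone or email contact or a physician visit". Voluntary withdrawal and death carry no asterisk. A separate paragraph has site staff contact any subject who misses a visit, in order to establish and document the reason.

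NOSE is described in Section 3.3 as a five-item Likert instrument. Section 8.2 lists it among the baseline data as "NOSE questionnaire (completed by the subject". Table 1 places it at baseline and at the 4-, 12- and 26-week visits, the last with a window of 14 days either side. The plan describes no remote or out-of-visit NOSE.

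Section 13.3 analyses the endpoints on all treated subjects. Section 13.8.2 makes a general commitment to collect every data point and tests the hypothesis on available data. If any primary values are missing, the first further analysis consists of "treating all missing data points for the primary endpoint as 0 improvement". If that does not uphold the conclusion, multiple imputation follows, using the baseline, 4-week and 12-week scores.

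**The concern.** The plan already pays for a contact with some subjects who would otherwise have no 26-week outcome, yet it does not ask for the one item that decides the trial. NOSE needs no examination and no equipment. A site that follows Section 10 and Table 1 to the letter can speak to a subject at week 26, record adverse events or the reason for the missed visit, and leave the primary endpoint blank.

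The design makes this matter. The trial is single-arm, its only efficacy measure is patient-reported, and the main test uses available cases. If subjects without a 26-week score improved less than those with one, the available-case mean is too high, and there is no control arm in which differential loss would show. Section 13.8.2 deals with missing values after the fact. Collecting some of them would prevent the problem.

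**Working it through.** **Inputs.** Performance goal 15: "The objective is to show that the mean improvement in NOSE score from baseline to 26 weeks exceeds 15 points" (Section 13.2). Section 13.1: "Prior study data was used to estimate the expected mean change (28.5) and standard deviation (30.3) for the change in NOSE score". Test level, Section 13.2: "The hypothesis is tested at the one-sided alpha 0.05 level". Attrition, Section 13.1: "To allow for up to 10% attrition, a total of 50 subjects will be enrolled". The number of missing scores that could be recovered is not given, so the full range of 0 to 5 out of 5 is shown.

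**1. The plan's own figure.** Section 13.1 states: "N=45 subjects would provide 90% power to test the study hypothesis at the one-sided alpha level of 0.05". For a one-sample t-test, power = P(T > t(0.95, n−1)), where T is noncentral t with n−1 degrees of freedom and noncentrality (28.5 − 15)/30.3 × √n. At n = 45 the noncentrality is 13.5/30.3 × 6.708 = 2.989 and power is 90.3%. The smallest n with at least 90% power is 45, and 45/0.90 = 50. The design reproduces.

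**2. Power over the recoverable range.** Of 50 treated, 5 lack a 26-week score before any recovery. The available-case column is the formula above. The other column is by simulation (200,000 trials of 50, normal changes, missingness unrelated to outcome, missing values set to 0). Its expected mean is 28.5 × (50 − m)/50 with m missing.

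| Recovered of 5 | Still missing | Available-case power | Mean with missing = 0 | Power with missing = 0 |
|---|---|---|---|---|
| 0 | 5 | 90.3% | 25.65 | 81.2% |
| 2 | 3 | 91.4% | 26.79 | 87.1% |
| 3 | 2 | 91.9% | 27.36 | 89% |
| 5 | 0 | 92.8% | 28.50 | 92.9% |

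**3. Bias in the available-case mean.** Suppose 45 completers average 28.5 and the 5 missing subjects truly average between 0 and 15 (an assumed range).

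- At 0: (45 × 28.5 + 5 × 0)/50 = 25.65, so the available-case mean is 28.5 − 25.65 = 2.85 too high.
- At 15: (45 × 28.5 + 5 × 15)/50 = 27.15, so it is 28.5 − 27.15 = 1.35 too high.

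**4. False success in the extreme case.** Let the overall true mean be exactly 15 and all 5 leavers have zero improvement. Completers then average 15 × 50/45 = 16.67. The noncentrality is 1.67/30.3 × √45 = 0.37, and the nominal 5% available-case test rejects 10.0% of the time. With 2 missing, completers average 15 × 50/48 = 15.63 and the rate is 6.6%. In the same scenarios the missing = 0 analysis, by simulation, rejects about 4.5% with 5 missing and 4.8% with 2.

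**The case against.** Much of the case on the other side stands.

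- **Section 10 does not forbid NOSE.** It says what safety follow-up will include, and Section 13.8.2 promises full efforts at data collection. A reader might infer that the plan restricts the contact to adverse events; the text does not say so. What remains is that no mechanism is given, and sites work from Section 10 and Table 1.
- **Lost subjects are mostly out of reach.** Loss to follow-up requires three failed contact attempts as well as lateness of more than a month beyond the window. Lateness alone is not a withdrawal category, and a subject who attends a later visit stops being lost. It would be wrong to say that the plan discards obtainable data from lost subjects in general. The recoverable scores come mainly from physician-withdrawn subjects and from reachable subjects who miss week 26. The latter fall under the missed-visit paragraph, not the safety-contact sentence.
- **Voluntary withdrawals** are perhaps the likeliest to have been disappointed, and the safety contact does not cover them.
- **The attrition is budgeted.** The primary test keeps 90.3% power with 45 completers. A reader might take the 81% as the chance of study success. It is the power of a sensitivity analysis, which multiple imputation follows if it fails.
- **The 10.0% is an extreme case**, and the plan's own missing = 0 analysis brings the rate below 5% there.
- **Mode.** A score read out by site staff over the phone in an open trial is not the same as self-completion. The documents give no size for this effect.

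**Conclusion.** The gap is real and limited. The plan foresees contact with subjects who may lack a 26-week NOSE score and does not provide for asking for it. The stated sample size is unaffected.

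At the planned attrition, full recovery would raise available-case power by at most 2.5 percentage points (90.3% to 92.8%) and that of the missing = 0 analysis by about 12 (81.2% to 92.9%). With no recovery the gain is nil. The more useful benefit is less dependence on untestable assumptions: a potential upward bias of 1.35 to 2.85 points under the assumed range for the missing subjects.

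These figures rest on the plan's mean and standard deviation, normal changes, and 5 missing of 50, which is the plan's upper allowance and not a forecast. The documents do not support a claim that the trial's success is in jeopardy or that its false-success rate is inflated without any check. This is a cheap improvement to data collection, not an error in the analysis.

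**What to change.** In Section 10, with a matching note to Table 1, state that:

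- where the subject agrees, the subject-completed NOSE form will be obtained by email, mail, phone or visit at the 26-week time point, within the existing 14 days either side, from subjects who do not attend or who have been withdrawn by the physician;
- the form will be offered at exit to voluntary withdrawals who agree;
- date and mode of completion will be recorded, with self-completion preferred over staff-read phone administration.

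In Section 13.8.2, state that an in-window score counts as the primary endpoint value whatever its mode, that earlier scores enter only the multiple-imputation model, and that the primary analysis will be repeated without remote scores.

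The cost is a few sentences, a remote version of an existing form and one extra analysis. No visit is added, and neither the sample size nor clinical management changes. The downside is a possible difference by mode of administration, which the preference for self-completion reduces and the repeat analysis would help to show.
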